1.0 TRIAL DESIGN

1.1 Trial Design

This is a single institution, single-arm, phase II trial of perioperative combination immunotherapy (nivolumab + ipilimumab) in patients with resectable malignant peritoneal mesothelioma. All patients will undergo pretreatment cross-sectional imaging (CT or MRI) for clinical staging, as well as a laparoscopy to stage the peritoneum, assess resectability, and acquire pretreatment tissue, all of which is part of standard of care. Enrolled patients will then receive neoadjuvant combination immunotherapy, which will include 2 doses of nivolumab (3 mg/kg IV every 21 days) and 1 cycle of ipilimumab (1 mg/kg IV). Repeat cross-sectional imaging (CT or MRI) will be performed to assess response to neoadjuvant immunotherapy. Surgical intervention via cytoreductive surgery (CRS) and hyperthermic intraperitoneal chemoperfusion (HIPEC) with mitomycin-C will occur 2-6 weeks following the last dose of the neoadjuvant therapy, at which point additional pathologic assessments will be made. About 6-8 weeks following surgery and after new baseline cross-sectional imaging is completed, patients will receive adjuvant ipilimumab (2 cycles; 1mg/kg IV every 6 weeks) + nivolumab (1 year). Restaging cross sectional scans will be obtained to assess response every 6 weeks while on adjuvant therapy and every 3 months for an additional year after completing therapy.

The primary objective of the study is to assess the rate of major pathologic response (MPR), defined as $\leq 10\%$ residual viable tumor (RVT) in the resected surgical specimen following neoadjuvant nivolumab + ipilimumab. Secondary objectives include assessment of the safety profile and feasibility of the neoadjuvant regimen, radiologic response rate, and overall and progression-free survival. Samples will be obtained pretreatment via laparoscopy and after nivolumab + ipilimumab treatment at surgical resection. Additional correlates will be assessed including immune status/infiltration of the tumor, CA-125 serum levels, serum SRMP (soluble mesothelin-related peptide), circulating tumor cells, as well as radiologic correlates.

1.2 Trial Schema

2.0 OBJECTIVES

2.1 Primary Objectives

1. To determine pathologic response of the tumor to neoadjuvant treatment with nivolumab + ipilimumab via Major Pathologic Response (MPR), defined as ≤10% residual viable tumor (RVT) cells, as well as grade, necrosis, and Ki67.

2.2 Secondary Objectives

1. To determine the safety profile of neoadjuvant nivolumab + ipilimumab, as defined by rate of grade III/IV adverse events according to CTCAE v5.0, occurring up to 30 days post-operatively.
2. To determine feasibility of neoadjuvant nivolumab + ipilimumab, as measured by the number of participants who complete neoadjuvant treatment with nivolumab + ipilimumab and proceed to surgery without extended treatment-related delay (> 6-week delay) or progression precluding surgery.
3. To determine the Overall Survival (OS) effect from neoadjuvant nivolumab + ipilimumab, defined as time from enrollment on study to death from any cause.
4. To determine the Progression-free Survival (PFS) effect from neoadjuvant nivolumab + ipilimumab, defined as time from enrollment on study to disease progression or death.

5. To determine the safety profile of adjuvant nivolumab + ipilimumab after cytoreductive surgery and HIPEC.
6. To determine the radiologic response to neoadjuvant nivolumab + ipilimumab utilizing RECIST 1.1 pre- and post-treatment.
7. To determine the effect of neoadjuvant nivolumab + ipilimumab on peritoneal carcinomatosis index (PCI).

2.3 Exploratory Objectives

1. To determine immune status/infiltration of the tumor in response to neoadjuvant nivolumab + ipilimumab, including the change in presence of TILs/macrophages (CD3, CD4, CD8, CD11b, CD68, CD20) and PDL1 status.
2. To determine blood-based changes with nivolumab + ipilimumab treatment, including PBMC inflammation expression profile, serum mesothelin (SMRP), osteopontin, CA-125, and circulating tumor cells.
3. To evaluate health-related quality of life (HRQoL) for patients with peritoneal mesothelioma undergoing perioperative immunotherapy, measured by the EORTC QLQ C30, which was developed specifically to assess quality of life in patients with cancer.
4. To correlate radiologic tumor measurements based on RECIST 1.1 and tumor volume with patient survival.
5. To relate pathologic assessment of immune infiltrate with pre-operative image-based tumor signatures.
6. To assess the response of neoadjuvant immunotherapy in those with BAP1 mutations identified on next-generation sequencing.

3.0 BACKGROUND

3.1 Pharmaceutical and Therapeutic Background

The importance of intact immune surveillance in controlling outgrowth of neoplastic transformation has been known for decades. Accumulating evidence shows a correlation between tumor-infiltrating lymphocytes (TILs) in cancer tissue and favorable prognosis in various malignancies. In particular, the presence of CD8+ T-cells and the ratio of CD8+ effector T-cells / FoxP3+ regulatory T-cells seems to correlate with improved prognosis and long-term survival in many solid tumors (Facciabene, 2012).

The PD-1 receptor-ligand interaction is a major pathway hijacked by tumors to suppress immune control. The normal function of PD-1, expressed on the cell surface of activated T-cells under

healthy conditions, is to down-regulate unwanted or excessive immune responses. PD-1 is an Ig superfamily member related to CD28 and CTLA-4 that has been shown to negatively regulate antigen receptor signaling upon engagement of its ligands (PD-L1 and/or PD-L2).

PD-1 was shown to be expressed on activated lymphocytes including peripheral CD4+ and CD8+ T-cells, B-cells, Tregs and Natural Killer cells. Expression has also been shown during thymic development on CD4-CD8- (double negative) T-cells as well as subsets of macrophages and dendritic cells. The ligands for PD-1 are constitutively expressed or can be induced in a variety of cell types, including non-hematopoietic tissues as well as in various tumors. Binding of either PD-1 ligand to PD-1 inhibits T-cell activation triggered through the T-cell receptor.

Although healthy organs express little (if any) PD-L1, a variety of cancers were demonstrated to express abundant levels of this T-cell inhibitor. PD-1 has been suggested to regulate tumor-specific T-cell expansion in subjects with melanoma, consistent with the understanding that the PD-1/PD-L1 pathway plays a critical role in tumor immune evasion and thereby is an attractive target for therapeutic intervention.

Nivolumab is a potent human immunoglobulin G4 (IgG4) monoclonal antibody (mAb) that binds to the PD-1 receptor and blocks its interaction with PD-L1 and PD-L2, releasing PD-1 pathway-mediated inhibition of the immune response, including the anti-tumor immune response.

The mechanism by which PD-1 down-modulates T-cell responses is similar to, but distinct from that of CTLA-4 as both molecules regulate an overlapping set of signaling proteins. CTLA-4 is a negative regulator of T-cell activity. Ipilimumab is a monoclonal antibody that binds to CTLA-4 and blocks the interaction of CTLA-4 with its ligands, CD80/CD86. Blockade of CTLA-4 has been shown to augment T-cell activation and proliferation, including the activation and proliferation of tumor infiltrating T-effector cells. Inhibition of CTLA-4 signaling can also reduce T-regulatory cell function, which may contribute to a general increase in T cell responsiveness, including the anti-tumor immune response.

Combined nivolumab (anti-PD-1) and ipilimumab (anti-CTLA-4) mediated inhibition has also been shown to result in enhanced T-cell function that is greater than the effects of either antibody alone, suggesting a synergistic effect of the combination, and results in improved anti-tumor responses in metastatic melanoma and advanced RCC. In murine syngeneic tumor models, dual blockade of PD-1 and CTLA-4 resulted in increased anti-tumor activity (Fiegle, 2019).

3.2 Rationale

3.2.1 Rationale for the Trial and Selected Subject Populations

Around 500-800 new cases of peritoneal mesothelioma occur every year in the United States (Miura, 2014). In contrast to pleural mesothelioma, an antecedent exposure to asbestos cannot always be found in patients with this disease. However, we previously demonstrated that germline mutations (with *BAP1* mutations being most common) are found in as many as 25% of peritoneal mesothelioma patients, compared to only 7% of those with pleural disease (Panou, 2018), implying that inherited susceptibility may play a larger role in peritoneal mesothelioma. Patients generally present with ascites or malignant bowel obstructions, which are significantly life limiting due to the resulting malnutrition and inanition. Cross sectional imaging such as CT scans or MRIs are

utilized in the diagnosis of peritoneal mesothelioma but they generally underestimate the burden of disease. There are 3 major histologic subtypes of mesothelioma: epithelial, sarcomatoid, and mixed or biphasic (Husain, 2009). Pathologic subtype is one of the most important prognostic indicators in this disease, so an accurate determination of pathology is essential (Rusch, 2012).

The prognosis of patients with peritoneal mesothelioma is rather dismal in the absence of treatment, with a median survival of 12 months (Alexander, 2013). The standard of care for patients with peritoneal mesothelioma is the performance of cytoreductive surgery (CRS) and hyperthermic intra-peritoneal chemotherapy (HIPEC). The surgery consists of extirpation of peritoneal tumor with parietal and visceral peritonectomy procedures and visceral resections as necessary. During the surgery, the burden of disease is assessed by the peritoneal cancer index (PCI score). This score is measured by dividing the abdomen into 13 zones (including 4 zones for the bowel) and ranges from 0-39 (39 being the most disease). At the end of the operation the residual tumor is assessed by the completeness of cytoreduction which is an important prognostic factor for the survival of these patients. Heated chemotherapy is then applied to the peritoneal surfaces for 90 minutes and circulated at 600 ml-1500ml/min at 42 °C (Turaga K 2016).

Patients undergoing CRS+HIPEC have an overall median survival of 53 months, with a more favorable prognosis for patients that undergo a complete cytoreduction (CC-0/1)(Yan TD 2009). The agent of choice for the intra-operative chemotherapy is either platinum based (cisplatin/carboplatin) or mitomycin C (Helm, 2015). Grade III-IV complication rates after this surgery can be as high as 31-40% (Kepenekian 2016). Major complications include death, anastomotic leak, deep or superficial site infection, anemia, re-operations, organ failure including renal failure, cardiac failure or respiratory failure, neutropenia, thromboembolic events, dehydration and failure to thrive.

Due to the relatively low incidence of peritoneal mesothelioma, there are no large randomized controlled trials for either surgery or chemotherapy to guide management, leaving no clear consensus on optimal treatment approach. Therefore, much of the management is extrapolated from the studies in pleural mesothelioma. Standard chemotherapy for pleural mesothelioma consists of pemetrexed plus cisplatin. This regimen was FDA-approved for MM based on a single-blind, placebo-controlled, phase III trial, which randomized 456 patients to cisplatin with or without pemetrexed. Patients who received the combination achieved a longer median overall survival (12.1 vs. 9.3 months, $p = 0.020$), a superior time to progression (5.7 vs. 3.9 months, $p = 0.001$), and a higher objective response rate (41% vs. 17%, $p < 0.001$) than patients who received cisplatin alone (Vogelzang, 2003).

However, the benefits of cytotoxic chemotherapy for peritoneal mesothelioma are less clear and alternative therapies such as immunotherapy warrant investigation. PD-1/PD-L1 and CTLA4 are immune checkpoints that mediate immune evasion in a wide spectrum of tumors. While the normal function of PD-1 and CTLA4 is to counteract excessive immune responses directed against normal tissues, various types of cancer have manipulated this function by up-regulating the natural ligands of these checkpoints to evade immune recognition. The critical role of this pathway became evident with the promising results of clinical trials of PD-1/PD-L1 and CTLA4 inhibitors, such as pembrolizumab (Hamid, 2013), nivolumab (Wolchok, 2013), and MPDL3280A (Powderly, 2013). While immune checkpoint blockers have not been evaluated in mesothelioma in the neoadjuvant setting, they are being used safely in the preoperative setting in a variety of tumor types.

In an analysis presented at ASCO 2014 (Kindler, 2014), we analyzed gene expression data on 44 malignant mesothelioma tumors (Gordon, 2005), applied a melanoma-derived signature of T-cell inflammation (Harlin, 2009), and analyzed other immune response related genes. We identified that 32% of malignant mesotheliomas showed high CD8 gene expression, and a T-cell inflamed phenotype analogous to melanomas was present in multiple tumors.

We evaluated MM tumor tissues from patients by multi-color immunohistochemistry (IHC), staining for CD68 (macrophages), CD8 (tumor infiltrating lymphocytes), and PD-L1 (immune checkpoint, MTA: [name]) We observed PD-L1 expression in 75% of MM tumors tested, which was 2-3+ in 37.5%, and 1+ in 37.5%. Patchy higher level PD-L1 expression was observed in stromal or CD68 cells located close to CD8+ cells. CD8 tumor infiltrating lymphocytes (TILs) were present in all epithelial tumors. Prominent CD68 infiltration was seen in all tumors. Thus, we identified high PDL-1 expression, a CD8 infiltrative pattern with a T-cell inflamed expression, and presence of PD-1/PD-L1 immune checkpoints in a subset of MM (approximately 1/3 of MM tumors) similar to the phenotype found in other tumors such as melanoma that benefit from immune checkpoint blockade. Furthermore, we recently identified a marked heterogeneity in PD-L1 expression specifically in peritoneal mesothelioma associated with either systemic or intraperitoneal chemotherapy administration (White, 2020). This demonstrates the pliability of PD-L1 as a biomarker, indicating that a low PD-L1 status at a single timepoint should not preclude patients from immune checkpoint inhibition therapy.

Based on these and other studies, MM is an ideal target disease for anti-PD-1 therapy, and further investigation of the biology of this agent in this disease is warranted. This hypothesis is further supported by the recently reported data from the CheckMate 743 study. This was a randomized, open-label trial in patients with unresectable malignant pleural mesothelioma, with a primary endpoint of overall survival. Patients were randomized to receive either combination immunotherapy with nivolumab + ipilimumab for up to 2 years or standard chemotherapy with pemetrexed + either cisplatin or carboplatin for 6 cycles. The trial demonstrated a statistically significant improvement in OS for patients randomized to immunotherapy compared to chemotherapy. While it was efficacious in all histologies, there was a greater benefit noted in the sarcomatoid subgroup. The results of this trial have established a new standard of care in the treatment of malignant pleural mesothelioma, with immunotherapy now considered first line therapy. (Baas 2020).

Therefore, we expect to see a similar response to immunotherapy in the peritoneal disease setting, and with this study we aim to evaluate that response. Of note, while resection is typically offered only to patients with non-sarcomatoid histology, in this trial we plan to include sarcomatoid histologies as well. Due to the robust response in the CheckMate 743 trial, which demonstrated that immunotherapy allowed for an equivalent survival in the sarcomatoid cohort to the epithelioid cohort, we anticipate that the sarcomatoid peritoneal patients will have a similar response, making their disease more amenable to cytoreduction.

3.2.2 Rationale for Endpoints

Tumor response is a surrogate marker of benefit from immune therapies that has been used for studies with nivolumab, ipilimumab, and other immune therapies. Response is considered a reliable marker of benefit for malignant mesothelioma and correlates with a survival benefit

(Blayney, 2012). Response in pleural mesothelioma is generally assessed via the modified RECIST 1.1 criteria for assessment of response in mesothelioma (Armato 2018). However, radiologic assessments of tumor response in peritoneal disease are poor and usually underestimate the burden of disease.

Retrospective analyses have revealed that Major Pathologic Response (MPR) after neoadjuvant chemotherapy was related to improved overall survival and disease-free survival. Chaft *et al.* examined neoadjuvant chemotherapy for non-squamous NSCLC (non-small cell lung cancer) and reported that 22% of tumors showed MPR, with these responses being associated with long-term survival. Furthermore, MPR has since been used in several prospective and randomized studies and has now been recommended as a surrogate endpoint specifically in the context of neoadjuvant immunotherapy (Hellmann, 2014). Pathologic responses, such as MPR and pathologic complete response are to date the most commonly used metrics for assessing response to neoadjuvant immunotherapy, and have been used in trials for melanoma, colon cancer, NSCLC, muscle-invasive bladder cancer, and several others (Chalabi, 2020; Yang, 2020). Patients with non-small cell lung cancer who received neoadjuvant nivolumab were found to have a 45% rate of MPR (Bott, 2019), and 30% of those with resectable stage III/IV melanoma who received just a single dose of pembrolizumab had MPR, 100% of which had a durable disease-free survival at 24 months (Huang, 2019). This pathologic response is seen not only in those with known susceptibility to immunotherapy, such as those with mismatch repair deficient (dMMR) tumors. In the NICHE study, though colorectal cancer patients with dMMR tumors had a 95% MPR rate, those with MMR-proficient tumors still had a robust response with 20% MPR rate (Chalabi, 2020).

4.0 SUBJECT SELECTION AND WITHDRAWAL

4.1 Number of Subjects

This is a single-center phase II study and will enroll 37 patients for a total of 42 months. The University of Chicago will attempt to enroll 18-19 patients each year for two consecutive years.

4.2 Gender, Age, Racial and Ethnic Origin of Subjects

Both male and female patients who are at least 18 years of age, of any ethnic or racial background, are included. Children (≤ 18 years of age) will be excluded from this study to limit variability in the study population and avoid this vulnerable population. There is no restriction on the racial or ethnic origin of subjects. Please see the inclusion and exclusion criteria for full details. Prospective approval of protocol deviations to recruitment and enrollment criteria, also known as protocol waivers or exemptions, is not permitted.

4.3 Inclusion Criteria

In order to be eligible for participation in this trial, the subject must:

1. Have a diagnosis of histologically or cytologically confirmed peritoneal mesothelioma, of epithelial, biphasic, or sarcomatoid subtypes
2. Have disease burden amenable to cytoreduction and hyperthermic intraperitoneal chemotherapy (HIPEC), as determined by a surgeon specializing in mesothelioma

3. Have measurable or evaluable disease based on RECIST 1.1 or on laparoscopy
4. Have no definitive evidence of visceral metastases by best staging
5. Be willing to undergo laparoscopy or mini-laparotomy for peritoneal staging
6. Demonstrate adequate organ function as determined by screening labs, with criteria defined in Table 1

Table 1. Adequate Organ Function Laboratory Values

System	Laboratory Value
Hematological	
Absolute neutrophil count (ANC)	$\geq 1,500 / \mu\text{L}$
Platelets	$\geq 100,000 / \mu\text{L}$
Hemoglobin	$\geq 9 \text{ g/dL}$
Renal	
Serum creatinine OR Measured or calculated ^a creatinine clearance (GFR can also be used in place of creatinine or CrCl)	$\leq 1.5 \times$ upper limit of normal (ULN) OR $\geq 60 \text{ mL/min}$ for subject with creatinine levels $> 1.5 \times$ institutional ULN
Hepatic	
Serum total bilirubin	$\leq 1.5 \times$ ULN
AST (SGOT) and ALT (SGPT)	$\leq 2.5 \times$ ULN
Coagulation	
International Normalized Ratio (INR) or Prothrombin Time (PT) Activated Partial Thromboplastin Time (aPTT)	$\leq 1.5 \times$ ULN. Patients on anticoagulation are expected to hold anticoagulation for at least 5 days prior to surgery.

^aCreatinine clearance should be calculated per institutional standard.

7. Have an ECOG performance status of < 2
8. Be ≥ 18 years of age on day of signing informed consent
9. Be willing and able to provide written informed consent for the trial

4.4 Exclusion Criteria

The subject must be excluded from participating in the trial if the subject:

1. Is currently participating in a study of an investigational agent and received an investigational agent within 4 weeks of the first dose of treatment on this protocol
2. Has received any immunotherapy agents outside of this protocol within 4 weeks of the first dose of treatment on this protocol

3. Has a diagnosis of immunodeficiency or is receiving chronic systemic steroid therapy (>10 mg of prednisone daily or equivalent) or any other form of immunosuppressive therapy within 14 days prior to the first dose of study drug.
4. Has a known history of active TB infection (*Bacillus tuberculosis*)
5. Has active COVID-19 infection
6. Has known history of, or any evidence of active, non-infectious pneumonitis that required steroids, or active pneumonitis
7. Has a severe hypersensitivity to nivolumab or any of its excipients
8. Has a severe hypersensitivity to ipilimumab or any of its excipients
9. Has an active autoimmune disease that has required systemic treatment in the past 2 years (i.e. with use of disease modifying agents, corticosteroids or immunosuppressive drugs)
10. Has a known additional malignancy that is progressing or required active treatment within the 3 years prior to enrollment - exceptions include basal cell carcinoma of the skin or squamous cell carcinoma of the skin that has undergone potentially curative therapy or in situ cervical cancer or other tumors that will not affect life expectancy
11. Has an active infection requiring systemic therapy
12. Has a known history of HIV, Hepatitis B, or Hepatitis C
13. Has known psychiatric or substance abuse disorders that would interfere with cooperation with the requirements of the trial.
14. Is pregnant or breastfeeding, or expecting to conceive or father children within the projected duration of the trial, starting with the screening visit through 120 days after the last dose of trial treatment
 - a. Female subjects of childbearing potential should have a negative urine or serum pregnancy within 72 hours prior to receiving the first dose of study medication. If the urine test is positive or cannot be confirmed as negative, a serum pregnancy test will be required.
 - b. Female subjects of childbearing potential should be willing to use 2 methods of birth control or be surgically sterile, or abstain from heterosexual activity for the course of the study through 120 days after the last dose of study medication (Reference Section 5.8.2). Subjects of childbearing potential are those who have not been surgically sterilized or have not been free from menses for > 1 year.

- c. Male subjects should agree to use an adequate method of contraception starting with the first dose of study therapy through 120 days after the last dose of study therapy.
- 15. Is on anticoagulation that cannot be discontinued in the perioperative period
- 16. Has received a live vaccine within 30 days of planned start of study therapy

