6.4.2 Prohibited Concomitant Medications

Subjects are prohibited from receiving the following therapies during the Treatment Phase of this trial:

- Immunotherapy not specified in this protocol
- Chemotherapy not specified in this protocol
- Investigational agents not specified in this protocol
- Radiation therapy
- Live vaccines within 30 days prior to the first dose of trial treatment and while participating in the trial. Examples of live vaccines include, but are not limited to, the following: measles, mumps, rubella, varicella/zoster, yellow fever, rabies, BCG, and typhoid vaccine.
- Systemic glucocorticoids while on nivolumab and ipilimumab for any purpose other than to modulate symptoms from an event of clinical interest of suspected immunologic etiology. The use of physiologic doses of corticosteroids may be approved after consultation with the Principal Investigator.

Subjects who, in the assessment by the treating investigator, require the use of any of the aforementioned treatments for clinical management should be removed from the trial. Subjects may receive other medications that the treating investigator deems to be medically necessary.

The Exclusion Criteria describes other medications that are prohibited in this trial.

There are no prohibited therapies during the Post-Treatment Follow-up Phase.

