7.5 Prior and Concomitant Medications Review

7.5.1 Prior Medications

The treating investigator or qualified designee will review prior medication use, including any protocol-specified washout requirement, and record prior medication taken by the subject within 28 days before starting the trial. Treatment for the disease for which the subject has enrolled in this study will be recorded separately and not listed as a prior medication.

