7.6.2 Prior Treatment Details

The treating investigator or qualified designee will review all prior cancer treatments including systemic treatments, radiation and surgeries.

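### Exclusion 1 misses patients who recently took a non-immunotherapy investigational agent and have left that study; separately, the MPR analysis takes no account of prior chemotherapy

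*Combined protocol and SAP*

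**What the plan says.** **Eligibility (protocol 4.4).** Item 1 excludes a patient who "Is currently participating in a study of an investigational agent and received an investigational agent within 4 weeks of the first dose" of study treatment. Item 2 excludes a patient who "Has received any immunotherapy agents outside of this protocol within 4 weeks of the first dose of treatment on this protocol". Item 3 includes a limit on "any other form of immunosuppressive therapy within 14 days prior to the first dose of study drug". No inclusion or exclusion criterion in 4.3 or 4.4 names prior chemotherapy. Section 4.2 does not allow waivers of the enrollment criteria, so the written wording decides who enters.

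**On-study restriction (6.4.2).** Chemotherapy outside the protocol is on a list introduced by "Subjects are prohibited from receiving the following therapies during the Treatment Phase of this trial". The list does not look back before the first dose, except for live vaccines.

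**History taken.** Under 7.6.2 the investigator or designee "will review all prior cancer treatments including systemic treatments, radiation and surgeries". Section 8 makes no use of that history.

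**Endpoint (2.1, 8.1).** MPR is at most 10% residual viable tumor in the resected specimen, and the primary objective treats it as response to the neoadjuvant combination. The definition refers neither to the pretreatment biopsy nor to earlier therapy. The trial has one arm and no stratification (6.2, 6.3).

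**The concern.** There are two distinct gaps.

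The first is a matter of logic. With the conditions joined by a conjunction, item 1 does not reach someone dosed with an investigational agent a week before study day 1 who has since left that study. If the agent was an immunotherapy, item 2 still applies; otherwise nothing does. The intent was probably broader than the wording, and with waivers barred the wording governs.

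The second is a matter of attribution. The protocol does not require untreated disease, and its own background describes peritoneal mesothelioma treated with systemic or intraperitoneal chemotherapy. A low percentage of viable tumor at resection does not show which treatment caused it. With no comparator and no use of treatment history in the analysis, regression left by earlier chemotherapy would count toward the MPR rate and toward rejecting the null of 0.5.

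**Working it through.** **Step 1. Who passes section 4.4 as written.** Each case concerns treatment within 4 weeks of the first dose.

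| Recent treatment | Still in that study? | Criterion reached | Excluded? |
|---|---|---|---|
| Investigational agent, any type | Yes | Item 1 | Yes |
| Investigational immunotherapy | No | Item 2 | Yes |
| Investigational agent, not immunotherapy | No | None by name | No |
| Standard immunotherapy | n/a | Item 2 | Yes |
| Standard chemotherapy | n/a | None by name | No |

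The conjunction in item 1 accounts for the third row only. The last row is a separate matter: no criterion addresses chemotherapy.

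**Step 2. Reproduce the plan's power.** From 8.1: N = 37, null 0.5, alternative about 0.7, one-sided exact binomial test, 80% power. Alpha is not stated.

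- One-sided 0.05: P(X ≥ 24 | 37, 0.5) = 0.0494, and P(X ≥ 23 | 37, 0.5) = 0.0939, so success means 24 or more. Power is P(X ≥ 24 | 37, 0.7) = 0.807, which matches the stated 80%.
- One-sided 0.025 (25 or more) gives power 0.698, and one-sided 0.10 (23 or more) gives 0.887. Neither matches.

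Alpha 0.05 is therefore inferred.

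**Step 3. Illustrate carry-over.** Let *f* be the share of patients with prior chemotherapy. Let *q* be the share of their would-be non-MPR cases that the earlier drug turns into MPR. With a true study-regimen rate of 0.50:

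observed rate = 0.50 + (1 − 0.50) × *f* × *q*

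false-positive rate = P(X ≥ 24 | 37, observed rate)

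| f | q | Observed rate | False-positive rate |
|---|---|---|---|
| 0 | 0 | 0.50 | 0.049 |
| 5% | 5% | 0.50 + 0.5 × 0.05 × 0.05 = 0.50125 | 0.051 |
| 10% | 5% | 0.5025 | 0.053 |
| 10% | 22% | 0.511 | 0.065 |
| 20% | 5% | 0.505 | 0.056 |
| 30% | 22% | 0.533 | 0.106 |
| 50% | 22% | 0.555 | 0.163 |

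Every *f* and *q* is assumed. The 22% is borrowed from 3.2.2, where a study of neoadjuvant chemotherapy in non-squamous lung cancer "reported that 22% of tumors showed MPR, with these responses being associated with long-term survival". It is neither a carry-over rate nor a peritoneal mesothelioma figure.

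**Step 4. What the calculation measures.** It models patients with any prior chemotherapy. It does not model the third row of the Step 1 table, whose size is unknown and probably small.

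**The case against.** **The size is assumed.** This stands. The documents give no expected share of pretreated patients and no chemotherapy MPR rate in this disease. Section 4.5 identifies patients at their initial oncology appointment, 3.2.1 calls cytoreductive surgery with HIPEC the standard of care, and it describes the benefit of cytotoxic chemotherapy here as less clear. None of this bars pretreated patients, but none of it supports a share as high as 50%. At low shares and carry-over the effect is close to nil. The model also allows only upward bias, whereas pretreated patients might respond less to the study drugs.

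**Other safeguards exist.** This stands in part. Item 3 and the blood-count limits in Table 1 may stop some recently treated patients, but neither names chemotherapy. Inclusion 3 requires measurable or evaluable disease, and the screening laparoscopy provides tissue, but the MPR definition does not use that biopsy.

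**Stronger readings that the documents do not support:**

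- A reader might infer that anyone given another anticancer drug just before day 1 is eligible. That is too broad: item 2 bars recent immunotherapy, and item 1 bars patients still in another study and dosed within 4 weeks.
- A reader might attribute the false-positive figures to the wording of item 1, or to a missing chemotherapy washout. They belong to prior chemotherapy at any time. Necrosis or fibrosis already present would remain after a washout, so an interval would not clearly remove the bias.
- A reader might take the reference in 7.5.1 to prior medication, "including any protocol-specified washout requirement", as proof that a chemotherapy washout was intended and then left out. Items 1, 2, 3 and 16 already supply time limits, so the reference has something to point to.
- A reader might infer that the paired PD-L1 comparison is confounded, because 3.2.1 reports "marked heterogeneity in PD-L1 expression specifically in peritoneal mesothelioma associated with either systemic or intraperitoneal chemotherapy administration". That comparison is exploratory and starts from the screening biopsy, so chemotherapy completed before it is part of the baseline. Only effects still evolving, or dosing after the biopsy, could matter, and the background gives no direction.

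**Conclusion.** Both gaps are real, and both are modest. Item 1 gives an eligibility result that was probably not intended for one narrow group: recent recipients of a non-immunotherapy investigational agent who have left that study. Independently, prior chemotherapy plays no part in eligibility or analysis, while the endpoint credits all regression seen at resection to nivolumab + ipilimumab.

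The size of any bias in the MPR rate cannot be determined from the documents. The illustrated range, 0.051 to 0.163 against a nominal 0.049, rests on the inferred alpha, a true rate of 0.50, and assumed shares and carry-over. It shows that the answer depends on how many pretreated patients enroll; it does not estimate the trial's error rate. It would be wrong to conclude that the primary test is invalid or that its error rate is known to be inflated.

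**What to change.** 1. **Section 4.4, item 1.** Reword so that receipt of an investigational agent within the item's own 4-week window excludes by itself, whether or not the patient is still in that study. This is a change to one sentence. It may turn away, or delay, the occasional patient.

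2. **Section 8.1.** Pre-specify, as a supportive estimate, the MPR rate with exact 95% CI in patients without prior systemic or intraperitoneal chemotherapy, using the history recorded under 7.6.2. Report the number of pretreated patients beside it. This costs one table row. The subset interval will be wider than the interval for all 37, so the row should be read as a check on consistency and not as a second test.

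Neither change alters N = 37, the success threshold of 24, the exact alpha of 0.0494 or the power of 0.807. Whether a chemotherapy-free interval before the first dose is needed is for the sponsor to decide. It is a trade-off that this point does not settle.
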